## **List of Abbreviations**

**AE:** Adverse event

**CRF:** Case report form

**DOVE:** Delivery of Opoid agonists for Ventilatory Emergencies

## Study Summary

Title	Assessing opioid overdose response framework for wearable medical devices
Short Title	DOVE
IRB Number	834304
Phase	Pilot Study
Methodology	
Part 1- is an exploratory study in which we will be conducting surveys of opioid users with the goal of being able to design a device to help the needs of this population. There could be a second visit in which participants are asked to give feedback on different device prototypes regarding how they look and how comfortable they are. Both visits could take place on the same day.
 
Part 2- evaluates a set of pilot prototype designs of devices that would be used in future studies to help detect when a person is close to a life-threatening overdose.

Study Duration	Two years from the date of enrollment.
Study Center(s)	Single-center

Objectives	
The primary objective is to determine the population's need for a wearable device that will treat an opioid overdose. Our goal is to obtain descriptive data and functional data on the use of a DOVE device prototype. Naloxone will not be administered during the trial. The DOVE device prototype is investigational. It has not been approved or cleared by the FDA.
 
Examples of data collected are:
 
 
• Study participant will be asked about their opioid use and overdose history.
 
• Accessibility to Naloxone
 
• Study participant will be asked to evaluate potential wearable device designs
 
• Study participant evaluates which devices would be more helpful in terms of detection and comfort
 
 
The secondary objective is to evaluate community availability status quo of opioid overdose reversal agents in patient population.
 
 
• Evaluate severity and prevalence of opioid overdoses within patient population.
 
• Assess frequency of opioid overdose.
 

Number of Subjects	
Part 1: Enrollment of approximately 100 subjects.
 
Part 2: Enrollment of approximately 50 subjects.

Main Inclusion and Exclusion Criteria	
Inclusion Criteria
 
 
• Males and Females
 
• 21 years of age or older
 
• Have used opioids for more than 3 months or will be having surgery where opioids will be administered.
 
• Able to provide informed consent
 
• Moderate to severe chronic pain treated (by prescription or illicitly) with opioids or recreation use
 
 
Exclusion Criteria
 
 
• Pregnancy
 

Investigational Product	
For Part 1 there could be a second visit in which we ask patient's feedback on different device prototypes regarding how they look and how comfortable they are. Both visits could take place on the same day. The device will not function while you are wearing it.
 
For Part 2 the DOVE prototype device is a wearable device. Subjects will be asked to wear the different prototypes of the device during the study visit to assess comfort and design. The device will not function while you are wearing it.

Statistical Methodology	
Survey answers will be entered into a RedCap database and responses will be aggregated and summarized using descriptive statistics. To compare differences survey responses among study participant subgroups, we will use t-tests or Wilcoxon rank-sum tests (F-tests or Kruskal-Wallis test) for continuous variables and Pearson chi square tests or Fisher's exact tests for categorical variables. Linear and logistic regression will be used to assess for differences in the continuous and dichotomous outcomes, respectively. All hypothesis tests will be two-sided using a two-sided alpha of 0.05 as our threshold for statistical significance. We will use Stata and/or SAS to analyze the data.

## BACKGROUND AND STUDY RATIONALE

This study will be conducted in full accordance with all applicable University of Pennsylvania Research Policies and Procedures and all applicable Federal and State laws and regulations including [as applicable] include the following regulations as they apply 45 CFR 46, 21 CFR Parts 50, 54, 56, and 812 and Good Clinical Practice: Consolidated Guidelines approved by the All episodes of noncompliance will be documented.

### 1 Introduction

In 2017, 70,237 people died following an accidental overdose in the United States. Of those, 47,600 (67.8%) died following an opioid overdose, a rate of one death every 11 minutes. Current trends predict that accidental overdose deaths continue rising, perhaps on an exponential trajectory.

[figure not shown]
While opioid overdoses affect almost all communities nationally, both rural and urban, Philadelphia is one of the most affected cities. Opioid overdose-related statistics are staggering and heartbreaking. Philadelphia County (City of Philadelphia) had the second highest rates of drug overdose deaths per county in 2016. Although nationally 68% of drug deaths involved opioids, more than 80% of drug deaths in Philadelphia involved opioids with an average of more than 3 fatal incidents per day. In the decade between 2007 and 2017, 5670 individuals died following an opioid overdose in Philadelphia. Until it plateaued in 2017, the number of fatal incidents increased every year.

## 1.1 Background and Relevant Literature

[figure not shown]
In many instances, tragic overdose deaths could be avoided. Within 5 minutes of an opioid overdose, an individual has irreversible brain damage caused by respiratory failure. Naloxone is a medication used to block the effects of opioids, especially in overdose. Naloxone may be combined with an opioid to decrease the risk of opioid misuse. When given intravenously, Naloxone works within two minutes, and when injected into a muscle, it works within five minutes; it may also be sprayed into the nose. The effects of Naloxone last about half an hour to an hour. Multiple doses may be required. If desired response is not obtained, doses should be repeated at 2 to 3 minute intervals. Without intervention, preventable deaths continue to occur [

Figure 1]. Life-threatening opioid overdose requires someone to assess breathing status and if needed, administer Naloxone [Figure 2].

**Figure 1: Overdose Progression with Naloxone Intervention**

**Figure 2: Overdose Progression without Naloxone Intervention**

At the time of opioid overdose, the person overdosing not only needs to have Naloxone available, but they need another person to administer the Naloxone, and quickly. Since someone is needed to administer, the bystander must also be trained or, at the minimum, comfortable administering the drug. While the American Heart Association added Naloxone administration as a special situation for the cardiopulmonary resuscitation (CPR) training in 2015, the median county training rates are generally low. In 2020, the median county training rate was just 2.39%. Still, the bystander must be able to access the patient. Since 1999, a patient was found alone following fatal overdose in 70,000 cases. While Naloxone is readily available today, many overdose victims are not found in time for administration of Naloxone. After five minutes without Naloxone intervention, a patient may continue to decompensate, become permanently disabled, or die. Despite Naloxone being broadly distributed and used as an overdose reversal agent since the 1970's, the rate of opioid overdose fatalities has only increased. Naloxone is thus a

solution, but not the solution. For Naloxone to be successful, drug delivery is dependent on variables that must be independent of variables that require human action.

While a strategy for the opioid epidemic could rely on increasing Naloxone accessibility, designers may also be inclined to reconsider how the medication is deployed. Two major strategies are (1) for more individuals to carry Naloxone and (2) for more distribution points for Naloxone. In Pennsylvania, Secretary of Health Rachel Levine issued a blanket standing order to permit over the counter Naloxone distribution: “this standing order may be used by Eligible Persons as a prescription or third-party prescription to obtain Naloxone from a pharmacy in the event that they are unable to obtain Naloxone or a prescription for Naloxone from their regular health care providers or another source.”

## **1.2 Name and Description of the Investigational Product**

### ***Device name: DOVE Prototype***

**Device Description:** The device is a de novo device called the DOVE (Delivery of Opioid agonists for Ventilatory Emergencies) Device. During part 2 of the study different prototypes of the device design will be evaluated without drug for comfort, fit, design, etc. The data collected will be preliminary data for a future study that aims to detect opioid overdose and inject Naloxone.

While the integration of a sensor to recognize opioid overdose and a direct reversal-agent response in a device is novel, predicate devices sense physiological variables and administer a drug in response to a change in the physiological variable. For example, the FreeO2 wearable device monitors hospitalized COPD patients by assessing SpO2. In response to SpO2 below the target range, the device adjusts a valve that changes O2 flow. Likewise, a sweat-based glucose monitor (EOFflow) has been proposed in conjunction with transdermal glucose delivery.

### ***Device category:***

Category B Device

### ***Intended use: During Part 2 we will evaluate different prototypes of the device.***

At a future time, the final DOVE device would be a wearable device that has components that can noninvasively sense overdose and administer commercially available opioid antagonist. DOVE would be substantially equivalent to the FreeO2 device in its continual assessment of a variable and threshold for response.

Ankle

[figure not shown]
Cannula

Wrist

Shoulder Deltoid

### **1.2.1 Nonclinical Data**

There is no animal model appropriate for testing the DOVE device, and therefore we have not done pre-clinical testing. Like FreeO2's pulse oximetry, DOVE would analyze physiologically associated waveforms and test whether those waveforms elicit a threshold that prompts the agent to response.

## **2 Study Objectives**

### **2.1 Primary Objective**

The primary objective of Part 1 is to determine the opioid user population's need for a wearable device that will treat an opioid overdose. The primary objective of Part 2 is to obtain descriptive data and functional data on DOVE device prototypes. Naloxone will not be administered during the trial. Examples of data collected are:

- Study participant will be asked about their opioid use and overdose history.
- Accessibility to Naloxone.
- Study participant will be asked to evaluate potential wearable device designs (Part 2 only).
- Study participant evaluates which devices would be more helpful in terms of detection and comfort (Part 2 only).

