## **3 Investigational Plan**

### **3.1 General Design**

The study will be a two-part, pilot study to evaluate feasibility and potential needs of opioid users. The study will obtain descriptive data on the use of the DOVE device prototype. Study population will consist of study participants who use opioids either after surgical procedure or recreationally. Part 1 will consist of a one-time short questionnaire. Healthy volunteers may be enrolled in Part 2 during the device modification phase. Part 2 can consist of more than one visit. At no point during in the study will Naloxone be administered.

**Part 1** will be an exploratory study, during which will administer questionnaires to develop a better understanding of factors influencing the needs of the population. Subjects could be given the option of completing part 1 and 2 in the same day.

**Part 2** is an exploratory study. Before the start of the device phase, subjects will be surveyed for comfort and subjective concerns. They will be shown the device and asked their opinion on design and comfort. The device may undergo minor modifications in response to functionality and subject comfort, and for iterative improvements such as the shape. We will test the device on participants for comfort, fit and design, using the results to improve the device, and then test the device again. This cycle will be continued until we have optimized the prototype device. We will record subject's verbal feedback, in order to guide the process of optimizing the device. At the end of Part 2, we will have optimized the design of the device for comfort and design preference. In part 2 there may be follow-up testing. Naloxone will not be administered during the study.

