## **8.1 Primary Endpoint**

For part 1 and 2 the primary objective is qualitative, only descriptive information will be obtained. The endpoint will be collection of feasibility and safety data.

As the primary objectives are descriptive and designed as a feasibility study, no power analysis will be performed. The sample size is one of convenience and limited by resources.

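### Does the Part 2 primary objective promise functional data that the plan never collects?

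*Combined protocol and SAP*

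**What the plan says.** The device objective appears twice. The Study Summary puts it as "Our goal is to obtain descriptive data and functional data on the use of a DOVE device prototype", and section 2.1 repeats the pair of data types for Part 2: "The primary objective of Part 2 is to obtain descriptive data and functional data on DOVE device prototypes". Neither place says what functional data are. Section 2.1 then lists examples of what will be collected, including this one: "Study participant evaluates which devices would be more helpful in terms of detection and comfort (Part 2 only".

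The Study Summary has Part 2 participants wear the prototypes "during the study visit to assess comfort and design. The device will not function while you are wearing it". Section 1.2 places sensing in a later product: "At a future time, the final DOVE device would be a wearable device that has components that can noninvasively sense overdose". It also says what the present data are for: "The data collected will be preliminary data for a future study that aims to detect opioid overdose and inject Naloxone".

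Section 3.2.1 gives two primary endpoints, one on comfort and tolerability and one on comfort and opinions of wearability. Section 7.4 provides a survey and an interview that leaves room for issues the team had not foreseen. Section 3.1 has verbal feedback recorded to steer the redesign, and adds: "The device may undergo minor modifications in response to functionality and subject comfort". Section 8.1 says that, for both parts, "the primary objective is qualitative, only descriptive information will be obtained", then names feasibility and safety information as the endpoint and explains why there is no power analysis. Section 8.4 assigns charts and narrative to the primary objective.

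**The concern.** An objective that names two kinds of data should lead to two kinds of measurement. Here the descriptive kind can be followed from objective to endpoint, questionnaire and summary. The functional kind stops at the objective. The usual meaning of functional data for a sensing device is how well it senses, and a prototype that is switched off while worn cannot supply that. Section 8.1, taken alone, appears to withdraw what section 2.1 promises.

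Two things would be at stake. First, nobody could say whether the Part 2 primary objective had been met. Second, participants' views on which design would help more with detection might be carried into the later overdose-detection study as if they were evidence on detection.

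**Working it through.** There is no stated power, effect size or derived sample size on this point, so there is no figure to reproduce. The check is a trace of the term, a count, and a comparison of possible readings.

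**Trace.** *Functional data* occurs in two places, the Study Summary (Objectives) and section 2.1. *Functionality* occurs in sections 3.1 and 3.1.2 (Study Design Phase), both times as a reason to modify the device. None of these gives a definition, an instrument or a method of summary.

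**Count.**
- Data types named for Part 2 in section 2.1: 2 (descriptive, functional). With a stated measure: 1.
- Primary endpoints in section 3.2.1: 2. On function: 0.
- Procedures in Table 1: 8 (eligibility review, consent, demographics and history, questionnaire, medications, dispensing, collection, adverse events). Marked at the Part 2 baseline visit: 5. Naming function: 0.

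The last count needs a control. The number of Table 1 rows that name comfort, fit or wearability is also 0 of 8. Those outcomes are collected all the same, under the generic questionnaire row. A zero in Table 1 therefore does not show that a topic goes uncollected, and this count cannot separate the functional data type from the descriptive one. The zero in section 3.2.1 does separate them, and it stands.

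**Section 2.1 beside section 8.1.** In 8.1 the words on descriptive information follow the statement that the objective is qualitative and lead into the absence of a power calculation. Read in that setting, they can mean that no inference will be made on the primary objective. Observations on function can be summarised descriptively like any others. The next sentence of 8.1 names feasibility as well as safety, which is wider than the two endpoints of 3.2.1 and can include usability. The two sections are compatible on this reading.

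**What each reading of *functional* would change.**
1. *Sensing or detection performance on the body.* Ruled out by the Study Summary (device not working when worn) and by section 1.2 (sensing belongs to a future device). No such data arise, and no analysis in section 8 asks for them.
2. *Function in use: attachment, handling, usability.* This suits the Study Summary's wording, which refers to use of a prototype. The questionnaire and interview of section 7.4 and the verbal feedback of section 3.1 can collect it, and section 8.4 summarises it.
3. *Checks off the body during redesign.* This suits the references to functionality in sections 3.1 and 3.1.2. It would be engineering input to the next prototype and not a participant outcome.

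Under all three readings the comfort, tolerability, wearability and design results come from the same participants, through the same instruments and with the same summaries.

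**Detection item.** A participant can say which design seems more helpful for detection without the device working. The answer is an opinion, and section 7.4 describes the Part 2 interview and survey as covering subjective experience.

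**The case for a change.** The strongest case for acting is that a term in a primary objective ought to have a definition in the protocol, and this one has none. Section 3.1 strengthens the case. It states the aim of obtaining data on use of the prototype in nearly the same words as the Study Summary but without *functional*, and it describes the end point of Part 2 as a design optimised for comfort and preference. The protocol is thus not consistent with itself on this word. Section 8.1 also calls the objective qualitative, which sits awkwardly with functional measurement. Section 19 allows publication of Part 2 as baseline data on the device, so a careless reader might take the detection opinions for more than they are.

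The inconsistency stands: the word is undefined, and its most natural meaning cannot apply to these visits. The stronger claims do not stand. A direct contradiction with section 8.1 depends on one of two fair readings of a single sentence. The claim that nothing collects functional data depends on excluding usability, which the text does not do. The feared misreading is already countered by the documents, which say that the prototype is not working and that detection is for later research. No section proposes a conclusion about detection from Part 2.

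**Conclusion.** This is a slip of wording with no effect on the results, and no change to the plan is needed. Its size is one undefined term in two places, leaving 1 of 2 named data types without a stated measure. The descriptive data type is untouched. Part 2 enrols about 50 people as a convenience sample with no power analysis (sections 4.5 and 8.3), so no sample size, test or power claim can shift. An analyst following sections 7.4 and 8.4 would summarise the questionnaire and interview material, including any remarks on how the prototype handles, and would present the detection item as participants' opinion of a device that was not working.

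The conclusion rests on two assumptions. The first is that *functional* does not mean measured sensing performance, which the Study Summary and section 1.2 support. The second is that the Part 2 questionnaire and case report form, which are not in the documents, contain nothing that would be reported as device performance. Nothing in the protocol points to such an item. If one existed, its meaning would have to be settled before reporting, but the comfort and design results would still stand.

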### **2.2 Secondary Objectives**

The secondary object of Part 1 is to evaluate community availability status quo of opioid overdose reversal agents in study participant population.

- Evaluate severity and prevalence of opioid overdoses within study participant population.
- Assess frequency of opioid overdose.

## **3 Investigational Plan**

### **3.1 General Design**

The study will be a two-part, pilot study to evaluate feasibility and potential needs of opioid users. The study will obtain descriptive data on the use of the DOVE device prototype. Study population will consist of study participants who use opioids either after surgical procedure or recreationally. Part 1 will consist of a one-time short questionnaire. Healthy volunteers may be enrolled in Part 2 during the device modification phase. Part 2 can consist of more than one visit. At no point during in the study will Naloxone be administered.

**Part 1** will be an exploratory study, during which will administer questionnaires to develop a better understanding of factors influencing the needs of the population. Subjects could be given the option of completing part 1 and 2 in the same day.

**Part 2** is an exploratory study. Before the start of the device phase, subjects will be surveyed for comfort and subjective concerns. They will be shown the device and asked their opinion on design and comfort. The device may undergo minor modifications in response to functionality and subject comfort, and for iterative improvements such as the shape. We will test the device on participants for comfort, fit and design, using the results to improve the device, and then test the device again. This cycle will be continued until we have optimized the prototype device. We will record subject's verbal feedback, in order to guide the process of optimizing the device. At the end of Part 2, we will have optimized the design of the device for comfort and design preference. In part 2 there may be follow-up testing. Naloxone will not be administered during the study.

### **3.1.2 Screening Phase**

Subjects will be recruited directly from clinics associated with the Hospital of the University of Pennsylvania, physician referrals, and IRB-approved advertisements targeting the Delaware Valley region. If a potential study participant is considered to be eligible, he/she will be referred to the research staff to participate in the initial telephone screening. A series of questions will be asked over the phone to confirm eligibility. Potential subjects that are eligible based on study criteria will be brought in for the baseline visit. Study participant may also be enrolled in clinic. The screening and baseline visit may occur on the same day.

### **3.1.2 Study Design Phase**

The wearable design phase (WDP) will consist of wearing the DOVE device for part 2. During part 1 subjects will not be required to wear the device. They would only be shown the device and asked their opinion on design and comfort.

In part 2, before the start of the wearable design phase, subjects will be surveyed for comfort and subjective concerns. The device may undergo minor changes in response to functionality and subject comfort. Subjects could be given the option of completing part 1 and 2 in the same day.

